9.2 Discussion of Study Design, Including Choice of Control Group

Study 270-201 is designed to be a first-in-man, phase 1/2 open-label, dose escalation study in patients with severe haemophilia A. Four doses of BMN 270 will be evaluated and the dose escalation decision tree for Cohorts 1-3 is summarized in Figure 9.1.1.

The decision to escalate to the next dose level will be made based on the review of safety parameters and FVIII activity by the Sponsor and the DRB.

There will be no control group. Parameters for each subject will be compared to a pre-treatment assessment of safety (liver function) and efficacy (number of bleeds, use of replacement therapy).

As AAV based treatment always leads to anti-capsid immune response, no true control group (for example with an empty AAV) is possible.

9.3 Selection of Study Population

Up to 15 severe haemophilia A patients may enroll into the study; the actual number of patients will depend on the criteria for dose escalation.

Additional criteria for participation in the study are provided in Section 9.3.1 and Section 9.3.2.

9.3.1 Inclusion Criteria

Individuals eligible to participate in this study must meet all of the following criteria:

- 1. Males that are 18 years or older with established severe Haemophilia A as evidenced by their medical history. Patients will be considered as severe if their base FVIII level is 1 IU/dL or less
- 2. Treated/exposed to FVIII concentrates or cryoprecipitate for a minimum of 150 exposure days (EDs)
- 3. Greater or equal to 12 bleeding episodes only if on on-demand therapy over the previous 12 months. Does not apply to patients on prophylaxis
- 4. Able to sign informed consent and comply with requirements of the trial
- 5. No history of inhibitor, and results from a modified Nijmegen Bethesda assay of less than 0.6 Bethesda Units (BU) 2 consecutive occasions at least one week apart within the past 12 months
- 6. Sexually active patients must be willing to use an acceptable method of contraception such as double barrier, including hormonal contraception for at least 6 months post-treatment. After 6 months, subjects may stop contraception use only if they have had 3 consecutive negative semen samples.

BOMARIN	270-201 – Amendment 5	Page 45
---------	-----------------------	---------

9.3.2 Exclusion Criteria

Individuals who meet any of the following exclusion criteria will not be eligible to participate in the study:

- 1. Detectable pre-existing immunity to the AAV5 capsid as measured by AAV5 transduction inhibition or AAV5 total antibodies
- 2. Any evidence of active infection or any immunosuppressive disorder.
- 3. HIV positive
- 4. Significant liver dysfunction as defined by abnormal elevation of:
 - ALT (alanine transaminase) to 3 times the upper limit of normal;
 - Bilirubin above 3 times the upper limit of normal;
 - Alkaline phosphatase above 3 times the upper limit of normal; or
 - INR (international normalized ratio) \geq 1.4.
- 5. Potential participants who have had a liver biopsy in the past 3 years are excluded if they had significant fibrosis of 3 or 4 as rated on a scale of 0-4
- 6. Evidence of any bleeding disorder not related to Haemophilia A
- 7. Platelet count of $< 100 \times 10^9/L$
- 8. Creatinine $\geq 1.5 \text{ mg/dL}$
- 9. Liver cirrhosis of any etiology as assessed by liver ultrasound
- 10. Hepatitis B if surface antigen is positive
- 11. Hepatitis C if RNA is positive
- 12. Treatment with any IP within 30 days prior to the end of the screening period
- 13. Any disease or condition at the physician's discretion that would prevent the patient from fully complying with the requirements of the study including possible corticosteroid treatment outlined in the protocol. The physician may exclude patients unwilling or unable to agree on not using alcohol for the 16-week period following the viral infusion.
- 14. Prior treatment with any gene transfer agent
- 15. Major surgery planned in the 16-week period following the viral infusion
- 16. Use of immunosuppressive agents or live vaccines within 30 days before the viral infusion

BOMARIN	270-201 – Amendment 5	Page 46
---------	-----------------------	---------

9.3.3 Removal of Subjects from Treatment or Assessment

Subjects may withdraw their consent to participate in the study at any time without prejudice. The Investigator must withdraw from the study any subject who requests to be withdrawn. A subject's participation in the study may be discontinued at any time at the discretion of the Investigator and in accordance with his/her clinical judgment. When possible, the tests and evaluations listed for the termination visit should be carried out.

BioMarin must be notified of all subject withdrawals as soon as possible. BioMarin also reserves the right to discontinue the study at any time for either clinical or administrative reasons and to discontinue participation by an individual Investigator or site for poor enrollment or noncompliance.

Reasons for which the Investigator or BioMarin may withdraw a subject from the study include, but are not limited to, the following:

- Subject requires medication or medical procedure prohibited by the protocol
- Subject does not adhere to study requirements specified in the protocol
- Subject was erroneously admitted into the study or does not meet entry criteria
- Subject is lost to follow-up

If a subject fails to return for scheduled visits, a documented effort must be made to determine the reason. If the subject cannot be reached by telephone, a certified letter should be sent to the subject requesting contact with the Investigator. This information should be recorded in the study records.

The Investigator or designee must explain to each subject, before enrollment into the study, that for evaluation of study results, the subject's protected health information obtained during the study may be shared with the study Sponsor, regulatory agencies, and IRB/IEC/REB. It is the Investigator's (or designee's) responsibility to obtain written permission to use protected health information per country-specific regulations, such as the Health Insurance Portability and Accountability Act (HIPAA) in the US, from each subject. If permission to use protected health information is withdrawn, it is the Investigator's responsibility to obtain a written request, to ensure that no further data will be collected from the subject and the subject will be removed from the study.

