12.10 End of Study

The study will end after the last subject completes the last Safety Follow-Up visit (Week 260). BioMarin reserves the right to discontinue the study any time for clinical or administrative reasons and to discontinue participation of an individual investigator or site for clinical or administrative reasons, including, but not limited to, poor enrollment or noncompliance with procedures of the protocol or GCP. In addition, the study may be terminated if, in the opinion of BioMarin, the safety of the study subjects may be compromised.

BOMARIN	270-201 – Amendment 6	Page 88
---------	-----------------------	---------

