PBMC collection for CTL baseline			X	
Von Willebrand Factor Antigen (VWF:Ag)	Х			
Direct Thrombin Test			X	
PCR of vector DNA in blood, saliva, urine, semen, and stools			X	
Biomarker testing ^f	Х			
Exploratory biomarker assessments ^g			X	
Haemo-QoL-A Quality of Life (QoL) assessment			Х	
BMN 270 Infusion				Х

Proprietary and Confidential

14 February 2017

BOMARIN	270-201 – Amendment 5	Page 36
---------	-----------------------	---------

^a Complete physical examination should be done at Screening. Brief physical examination may be done at Baseline and at the BMN 270 Infusion Visit. Height will be recorded at Screening only. Weight will be recorded at Screening and then every 6 months thereafter.

- ^b Includes baseline hFVIII activity (chromogenic FXa and one-stage APTT assays), hFVIII coagulation activity exploratory assay, hFVIII inhibitor level (Bethesda assay with Nijmegen modification), hFVIII total antibody titer, and hFVIII antigen (ELISA).
- ^c Screening (done during Screening) and testing (at Infusion Visit) of AAV5 pre-existing immunity may include plasma samples for 3 assays (in vivo transduction inhibition, in vitro transduction inhibition and AAV5 total antibody assays). Sample collection on the day of the infusion visit must be performed before the BMN 270 infusion is given.
- ^d Patients with documented negative results within the last 30 days do not need to be retested.
- ^e Refer to Table 9.7.8.2.1 for laboratory assessments to be included, and to Table 9.7.8.3.1 for liver function tests.
- $^{\rm f}$ Includes HLA genotyping, FVIII genotyping, TNF α and IL10a single nucleotide polymorphisms.
- ^g Blood samples will be collected from subjects to evaluate biochemical, molecular, cellular, and genetic/genomic aspects relevant to Haemophilia A disease. The exploratory genetic/genomic testing on these samples is optional.
- ^h Should the screening visit occur within 7 days of the drug infusion, physical examination, blood chemistry, LFTs, haematology, urine tests, coagulation screen, and CRP do not need to be repeated at Baseline.

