9.3.4 Subject Identification and Replacement of Subjects

Each subject will be assigned a unique subject identifier. This unique identifier will be on all CRF pages. In legal jurisdictions where use of initials is not permitted, a substitute identifier will be used.

Subjects who withdraw from the study will not be replaced.

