9.4.8 Prior and Concomitant Medications

All prescription and over-the-counter medications (including dietary and herbal supplements) taken by a subject for 30 days before Screening will be recorded on the designated CRF. The Investigator may prescribe additional medications during the study, as long as the prescribed medication is not prohibited by the protocol. In the event of an emergency, any needed medications may be prescribed without prior approval, but the medical monitor must be notified of the use of any contraindicated medications immediately thereafter. Any concomitant medications added or discontinued during the study should be recorded on the CRF.

BOMARIN	270-201 – Amendment 5	Page 51
---------	-----------------------	---------

The following medications are prohibited starting 30 days before Screening:

- Live vaccines
- Systemic immunosuppressive agents

Medications which are predominately metabolized by the liver (e.g., acetaminophen) and alcohol should, whenever possible, be avoided for the first 52 weeks of the study, and particularly within 48 hours prior to lab work.

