9.4.8.2.1 Therapeutic Corticosteroids

In general, therapeutic corticosteroids may be initiated when a subject's ALT value is $\geq 1.5x$ ULN, or based on review of FVIII and liver enzyme data after consultation between the Medical Monitor and the Investigator.

Reports of raised LFTs (defined as $ALT \ge 1.5x$ ULN) should be made to the BioMarin medical monitor within 30 minutes of the lab value being available. Local laboratory results of LFTs will be used to trigger corticosteroid treatment as needed. In case of discrepant results between local and central laboratories, the Investigator and Medical Monitor will decide further action.

Following initiation or completion of therapeutic corticosteroids, if ALT elevation $\geq 1.5x$ ULN is reported, steroid management decisions will based on discussions between the Investigator and Medical Monitor. Modification of the steroid regimen may take into consideration possible confounders for the ALT elevation and impact on FVIII expression.

BOMARIN	270-201 - Amendment 5	Page 52
---------	-----------------------	---------

Treatment with prednisolone will be initiated at a dose of 60 mg per day and then gradually tapered (60 mg daily for the first 2 weeks, then 40 mg the next 2 weeks, then 30 mg the next two weeks, then 20 mg the next two weeks, then 15 mg for the next week, then 10 mg for the next week, then 5 mg for the next week, then stop, for a total treatment of 11 weeks) (refer to Table 9.1.5).

After discontinuation of corticosteroids, weekly labs for ALT and FVIII levels will be measured once a week for 4 weeks to ensure stability in values.

Management and monitoring of reactions to corticosteroids should be determined by the Investigator's clinical judgment in consultation with the Sponsor's Medical Monitor. This includes the contraindicated use of NSAIDs during corticosteroid treatment, and specific monitoring not already covered by the schedule of events. Hepatitis B status and HCV viral load will be rechecked 6 weeks after the start of corticosteroid treatment, and then 1 week and 13 weeks after the completion of corticosteroid treatment. All adverse events should be reported as outlined in Section 10 of the protocol.

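### Section 9.3.3 lets already-infused subjects be withdrawn for prohibited medication, non-adherence or failed entry criteria, which stops no treatment and only ends their scheduled follow-up

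*Protocol*

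**What the plan says.** Section 9.3.3 (Amendment 5 text) introduces its list as "Reasons for which the Investigator or BioMarin may withdraw a subject from the study" and says that the list is not exhaustive. Three entries matter here: "Subject requires medication or medical procedure prohibited by the protocol", failure to adhere to study requirements, and "Subject was erroneously admitted into the study or does not meet entry criteria". The section heading speaks of removal from treatment or from assessment, but the text does not treat the two separately and does not mention whether the subject has been infused.

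Related provisions:

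- Section 9.3.4: "Subjects who withdraw from the study will not be replaced".
- Section 14.1.2: missing data are not imputed.
- Section 12.9: a subject who leaves before Week 260 is asked to attend one Early Termination visit.
- Sections 10.6 and 10.7: unresolved adverse events are followed to resolution or stability. After that, deaths and serious events are notified only if the investigator believes them related. Cancer, or a congenital anomaly in offspring, is notified if the investigator learns of it.
- Section 12.10: the sponsor may decide "to discontinue participation of an individual investigator or site for clinical or administrative reasons, including, but not limited to, poor enrollment". Neither this section nor 9.3.3 says what happens to subjects already dosed at that site.
- Section 9.4.8: "The following medications are prohibited starting 30 days before Screening", naming live vaccines and systemic immunosuppressive agents, with no end date. Section 9.4.8.2.1 then provides for raised ALT: "Treatment with prednisolone will be initiated at a dose of 60 mg per day and then gradually tapered".

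The Amendment 6 version of 9.3.3 is not in the part of the document at hand. The Amendment 6 revision table lists no change to it, and the Amendment 6 text of 10.6, 10.7, 12.9 and 12.10 is as described above.

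**The concern.** These removal reasons suit a trial with repeated dosing, where withdrawal can protect the subject from further drug. Here exposure is complete on Day 1 and cannot be reversed, and Section 9.1 regards re-treatment with this capsid as unlikely. A withdrawal for one of the three reasons after Day 1 therefore takes away observation and nothing else.

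The loss falls on the primary objectives. Section 8 puts safety first, then the dose needed for FVIII of at least 5 IU/dL at Week 16, including the duration of activity. Section 9.1 plans safety evaluation over about 5 years. Some of the protocol's own safeguards also depend on late sampling. Section 9.3.3.1 halts enrolment on repeated semen vector DNA beyond Week 52, and stopping contraception requires three consecutive negative semen samples. A withdrawn subject who had not yet cleared would have no scheduled samples to show either result.

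Late discovery of ineligibility is foreseeable. Table 9.1.1, footnote c, on the AAV5 assays says: "Sample collection on the day of the infusion visit must be performed before the BMN 270 infusion is given". This fixes when the sample is taken, not when the result must be known, and detectable AAV5 immunity is an exclusion criterion. How often this would happen is not stated.

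**Working it through.** **Planned follow-up (Section 9.3.5).** 4 weeks of screening + 16 weeks of post-infusion follow-up + 244 weeks of safety follow-up = 264 weeks, which reproduces the stated duration. Post-dose follow-up is 16 + 244 = 260 weeks.

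**Sample size (Section 14.7 in Amendment 6).** Up to 15 subjects. The Amendment 4 rationale reports 9 dosed, and Cohort 4 adds up to 6: 9 + 6 = 15.

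**Loss per removed subject**, as (260 − w)/260 for removal at Week w:

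- Week 16: 244/260 = 93.8%
- Week 52: 208/260 = 80.0%

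One subject is 1/15 = 6.7% of the trial and 1/6 = 16.7% of a full Cohort 4. One removal at Week 16 costs 244/(15 × 260) = 6.3% of all planned post-dose person-weeks.

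**What long-term follow-up can exclude.** With no events in n subjects, the one-sided 95% upper bound on the event rate is 1 − 0.05^(1/n):

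| Subjects followed | Upper bound |
|---|---|
| 15 | 18.1% |
| 14 | 19.3% |
| 13 | 20.6% |
| 6 | 39.3% |
| 5 | 45.1% |

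For an event with a true rate of 10%, the chance of seeing at least one case is 1 − 0.9^n: 79.4% at n = 15 and 74.6% at n = 13. Losing one or two subjects at random therefore costs a modest amount of precision.

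**If removal is related to outcome.** The counts here are assumed, because the documents give no withdrawal rate. Suppose 2 of 15 subjects would have a late event (13.3%, exact 95% CI 1.7% to 40.5%) and both are removed beforehand. Among those still followed the result is 0/13 (95% CI 0% to 24.7%). The removed subjects stay in the Safety population, so a crude incidence would read 0/15. Either way both events are missed, which matters more than the lost precision.

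**The immunosuppressant passages side by side.** Section 9.4.8 prohibits systemic immunosuppressive agents with no end date and no stated exception for corticosteroids given for raised ALT. Section 9.4.8.2.1 provides for prednisolone. Section 9.3.3 allows withdrawal when a prohibited medication is needed. Read literally together, a steroid-treated subject meets a withdrawal reason. Other parts show that this is not intended: Table 9.1.5 schedules tests during and after the steroid course, exclusion criterion 13 requires that a subject could undergo it, and Section 10.2.1 makes ALT-triggered steroid use a reportable event. The gap is one of wording, but it is there.

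**The case against.** The case for leaving the text alone has several sound parts.

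- *Withdrawal is optional.* The section permits removal and does not require it, and the text at hand reports no withdrawals. This stands, and it limits how serious the point is.
- *Some data still arrive.* The Early Termination visit covers LFTs, central FVIII, inhibitor, antibodies and, unless already cleared, PCR. Unresolved adverse events are followed. Section 10.3.1 runs adverse event reporting for about 5 years or until study discontinuation or termination, whichever is longer, although how that applies to a withdrawn subject is unclear. So follow-up does not end entirely, but none of this replaces scheduled visits.
- *Withdrawn subjects are still analysed.* They remain in the Safety population, and in the Full Analysis Set once they have a baseline and a post-baseline assessment. What is lost is later observation, not membership of the population.
- *The investigator needs discretion.* Section 9.3.3 also allows discontinuation on clinical judgement, and a correction should not abolish that.

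Three stronger readings are tempting, and the documents do not support them. A reader might infer that the rule selects subjects with liver events or low expression. Yet the protocol's responses to those outcomes, corticosteroids and on-demand FVIII (Section 9.4.8.1), are both provided for, so the quoted reason does not by itself target them. A reader might infer that steroid treatment triggers withdrawal, but the passages set out above show that this is not meant. A reader might also spread 15 subjects over the planned 6 to 10 sites to size the loss from closing one. That gives only an average per site, and a site closed for poor enrolment would probably hold fewer subjects, possibly none. Nor does the text say that they would be withdrawn.

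**Conclusion.** The point holds as a low-cost improvement, not as an error that invalidates the plan. Section 9.3.3 permits infused subjects to be withdrawn for three reasons that, after Day 1, protect nobody from further study drug and end the scheduled follow-up on which long-term safety and durability rest. Each removal at Week 16 would forgo 93.8% of that subject's post-dose follow-up, in a trial of at most 15 with no replacement and no imputation, and the data cannot be collected again.

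Bias arises only if removals are related to outcome. That is possible, but the documents do not show it, and they give no figure for how many subjects would be removed. The conclusion also assumes that 9.3.3 is unchanged in Amendment 6, as its revision table implies.

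**What to change.** Amend the wording as follows.

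1. In 9.3.3, state that once a subject has been infused, prohibited medication, non-adherence or failed entry criteria is recorded as a protocol deviation. The subject remains in the existing follow-up schedule through Week 260 unless he withdraws consent or permission to use his data, dies or is lost to follow-up. Keep the investigator's discretion to act for the subject's welfare, with continued safety follow-up offered where the subject agrees.
2. In 9.3.3 and 12.10, state that closing a site stops enrolment there and that its dosed subjects continue to be followed or are transferred.
3. Reconcile 9.4.8, 9.4.8.2.1 and 9.3.3 on systemic immunosuppressive agents. The clinical rule itself is for the sponsor to decide.

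The visits and assessments already exist, so the cost is amendment text, plus continued follow-up of the few deviating subjects who might otherwise have been withdrawn.

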9.3.3.1 Study Safety Evaluation Criteria

If any of the following events occur in a subject in the study who has received BMN 270 infusion, enrollment into the trial will be put on halt to complete an extensive safety analysis per Section 9.1.

Proprietary and Confidential

BOMARIN	270-201 – Amendment 5	Page 47
---------	-----------------------	---------

- Any ALT elevation > 5x ULN for at least 2 consecutive weeks after administration of BMN 270, in the absence of a definitive alternate etiology for the increase
- The occurrence of Grade 3 or higher adverse events (excluding ALT elevation) assessed as related to study drug, including liver failure and clinical hepatitis
- The detection of neutralizing antibodies to hFVIII following BMN 270 infusion
- The detection of AAV vector DNA in the semen of a participant in 3 consecutive samples (which are at least 2 weeks apart) more than 52 weeks after BMN 270 infusion, as discussed in Section 9.7.8.6
- The occurrence of a malignancy excluding skin cancers at any point after BMN 270 infusion

If the following event occurs in a subject in the study who has received BMN 270 infusion, a DRB review and analysis of safety data will be undertaken to determine whether the enrollment into the trial will be put on halt:

• Grade 2 adverse event assessed as related to study drug that persists for at least 7 days

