Subject 1 (Cohort 1) will be dosed by intravenous infusion with 6E12 vg/kg of body weight. If the FVIII activity level does not reach 5 IU/dL or greater (expressed as % in Figure 9.1.1) at the Week 3 visit in both assays, then no further subjects will be dosed in Cohort 1 and enrollment into Cohort 2 will initiate with Subject 2 at the next dose (2E13 vg/kg).

If the FVIII activity level in the first subject treated in Cohort 2 does not reach \geq 5 IU/dL at the Week 3 visit in both assays, then no further subjects will be dosed in Cohort 2 and enrollment into Cohort 3 (6E13) will initiate with the next subject.

If the FVIII activity level in the first subject treated in Cohort 3 does not reach \geq 5 IU/dL at the Week 3 visit in both assays, then the DRB will recommend whether to continue to add subjects to the cohort and/or whether to continue the study.

For the first subject treated in each of the first 3 cohorts, if the activity level reaches \geq 5 IU/dL and no safety issue is found, then up to four subjects will be enrolled in the Cohort, though the adaptive nature of this trial allows the DRB to recommend allocating subjects to the cohorts based on activity levels of FVIII and safety signals.

Cohort 4

For Cohort 4, 3 subjects will be enrolled at 4E13 vg/kg. If FVIII activity in these 3 subjects is \geq 5% at 8 weeks and if no safety issue is found, an additional 3 subjects may be enrolled in this cohort.

There will be an ongoing review of individual patient safety and efficacy data by the medical monitor and the Data Review Board (DRB). The adaptive nature of this trial allows the DRB Proprietary and Confidential 14 February 2017

BOMARIN	270-201 – Amendment 5	Page 34
---------	-----------------------	---------

to recommend allocating subjects to the cohorts based on activity levels of FVIII and safety signals.

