9.4.5 Method of Assigning Subjects to Treatment Groups

Subjects who meet all eligibility criteria (refer to Section 9.3.1 and Section 9.3.2) may be enrolled into the study. Approval by the Sponsor will be required prior to enrollment of each study subject. Upon their enrollment into the study, subjects will be assigned a unique subject number and dose level by the Sponsor.

Cohorts 1 to 3 are enrolled serially and their dose is defined in Section 9.4.6.2 below. Escalation is based on FVIII activity 3 weeks after injection. Cohorts may receive the next higher dose if subjects in the previous cohort does not meet the activity criteria, or the same dose if subjects in the previous cohort meets the activity criteria. Subjects in Cohort 4 will all be enrolled at a single dose.

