10.4.1.3 Persistent or Recurrent Adverse Events

A persistent AE (duration of adverse event > 7 days) is one that extends continuously, without resolution, between subject evaluation time points. Events that change in severity necessitate the recording of an additional AE. AEs that do not have a change in severity should be recorded only once on the eCRF.

BOMARIN	270-201 – Amendment 5	Page 66
---------	-----------------------	---------

A recurrent AE is one that occurs and resolves between subject evaluation time points, but then subsequently recurs. All recurrences of the AE should be recorded on the AE eCRF.

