15 DATA REVIEW BOARD

There will be no formal DMC for this study, however a safety and efficacy evaluation board (the Data Review Board [DRB]) composed of the investigator representatives and the Sponsor will be established.

The DRB will review safety and efficacy on an ongoing basis. The DRB will meet prior to dose escalation or dose expansion to assess available subject safety and efficacy data and make recommendations with regards to the conduct of study. Should a safety signal arise, including one which may warrant a halt of study enrollment, the DRB will promptly convene for further assessment of subject safety. Notification of all DRB meetings and meeting outcomes will be sent to participating sites.

BOMARIN	270-201 – Amendment 5	Page 90
---------	-----------------------	---------

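### Section 9.3.3.1: a related Grade 2 ALT rise of 7 to 13 days requires Data Review Board review, but an isolated related Grade 3 or 4 rise of that length meets no listed item

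*Protocol*

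**What the plan says.** Section 9.3.3.1 (Amendment 5; Amendment 4 has the same three items) works in two tiers. Three of its items can concern ALT.

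- Halt: "Any ALT elevation > 5x ULN for at least 2 consecutive weeks after administration of" BMN 270, unless another cause is definitively established.
- Halt: "The occurrence of Grade 3 or higher adverse events (excluding ALT elevation) assessed as related to study drug". Liver failure and clinical hepatitis are named as included.
- DRB review: "Grade 2 adverse event assessed as related to study drug that persists for at least 7 days". The lead-in makes this review mandatory; its purpose is to decide whether enrolment should be halted.

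The other halt items (neutralizing antibodies to FVIII, vector DNA in semen, malignancy) do not bear on ALT.

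Three supporting rules matter. Section 10.3.3.2 grades events by CTCAE v4. Section 10.4.1.4 makes a laboratory abnormality an adverse event if, for example, it changes concomitant therapy, as starting steroids would. Section 10.4.1.3 adds: "Events that change in severity necessitate the recording of an additional AE".

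The Amendment 6 body of Section 9.3.3.1 is not in the part of the protocol at hand. The Amendment 6 revision table in Section 24 lists no change to it.

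**The concern.** A list of safety triggers should ask for at least as much when the same event is worse. Here the ALT exclusion in the second item, the two-week duration in the first and the bare Grade 2 in the third combine so that, over one range of durations, the milder ALT rise draws a mandatory review and the more severe one draws nothing from the list.

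The Amendment 4 rationale explains two of these edits separately: item 3 relaxes the ALT halt, and item 7 moves the 7-day Grade 2 event from automatic halt to DRB review. Neither says that a higher-grade ALT rise should receive less than a Grade 2 one. The inversion looks like two reasoned edits that do not fit together.

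The liver is the safety focus of the study (Section 9.7.8), and Section 9.1 says re-dosing is unlikely. An infusion given to the next subject before review cannot be taken back.

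**Working it through.** The plan gives no figure to reproduce. The check applies the three items as logical conditions to an isolated, related ALT rise: no hepatitis, no liver failure, no definite other cause, and for Grades 3 and 4 no separate 7-day phase at Grade 2.

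- H1 (halt): ALT > 5 × ULN and duration ≥ 14 days.
- H2 (halt): grade ≥ 3, related, not ALT.
- R (review): grade = 2, related, duration ≥ 7 days.

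| Duration of ALT rise | Grade 2 | Grade 3 | Grade 4 |
|---|---|---|---|
| under 7 days | none | none | none |
| 7 to 13 days | review (R) | none | none |
| 14 days or more | review (R) | halt (H1) | halt (H1) |

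The last row assumes that the Grade 3 or 4 rise stays above 5 × ULN throughout. Only the middle row is inverted. It does not depend on the CTCAE cut-off for Grade 3 ALT: a rise of 7 to 13 days fails H1 on duration at any level, fails H2 by name and fails R on grade.

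**Outside ALT.** A related Grade 3 event of another kind lasting 10 days meets H2 and halts enrolment. The bare Grade 2 in R is harmless there, so the gap is specific to ALT.

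**Can Grade 2 in R be read as a floor?** The same section adds the words for a floor in H2 and omits them in R. Section 10.4.1.3 points the same way, since a change of grade starts a new record.

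**Illustrative mixed rise.** Take 4 days at Grade 2, 5 at Grade 3 and 4 at Grade 2.

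- Total at Grade 2 or above: 4 + 5 + 4 = 13 days.
- Separate records: 4, 5 and 4 days. The longest Grade 2 record is 4 < 7, so no review.
- Thirteen days wholly at Grade 2: 13 ≥ 7, so review.
- R changed to Grade 2 or higher, with no counting rule: the longest record is 5 < 7, still no review.
- R changed, with higher-grade days counted: 13 ≥ 7, review.

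**Other reading of the two weeks in H1.** Suppose two consecutive weekly samples above 5 × ULN suffice. Section 9.4.8.2 schedules local tests weekly in Weeks 1 to 36. If onset is uniform between samples (an assumption), a rise of d days, 7 ≤ d ≤ 14, covers two samples with probability (d − 7)/7:

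- d = 7: 0/7 = 0%
- d = 10: 3/7 = 43%
- d = 13: 6/7 = 86%

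The gap narrows but does not close.

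**Exposure.** Amendment 4 reports 9 subjects dosed (rationale, item 7). Section 9.3 caps enrolment at 15. At most 15 − 9 = 6 infusions remained from that point.

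**The case against.** The strongest case is that the protocol does not rely on Section 9.3.3.1 alone.

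- Section 9.4.8.2.1: reports of ALT at or above 1.5 × ULN "should be made to the BioMarin medical monitor within 30 minutes of the lab value being available".
- Section 10.2.1: an ALT rise that starts or changes steroids goes to the sponsor within 24 hours, whatever its severity.
- Section 10.3.3.2: Grade 4 events are reported as serious.
- Section 9.1: the medical monitor and DRB review individual data continuously, and Cohort 4 expands only if no safety issue is found.
- Section 9.4.5: "Approval by the Sponsor will be required prior to enrollment of each study subject".
- Section 15: "The DRB will meet prior to dose escalation or dose expansion to assess available subject safety and efficacy data". It also requires the DRB to meet promptly if a safety signal arises.
- Amendment 4 rationale, item 3: other causes will be weighed before later subjects are dosed after an ALT rise.

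Most of this stands. A reader might infer that a 10-day Grade 3 rise could go unnoticed, or that the DRB would have no occasion to look at it. The documents do not support that. A related Grade 3 or 4 ALT rise in a first-in-human, liver-directed study is hard to place outside any sensible meaning of a safety signal. But Section 15 does not define the term, and these general provisions cover Grade 2 rises as well. The sponsor still gave the Grade 2 event an explicit trigger.

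Two further objections stand in part. The two-sample reading of H1 would catch many of these rises, though item 3 of the Amendment 4 rationale describes the two weeks as a duration, which favours 14 days. And Section 10.4.1.3 is a recording rule that the protocol never ties to the clock in Section 9.3.3.1. The mixed-rise example depends on that link and on tests more frequent than weekly. The table does not.

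**Conclusion.** The point holds as a defect in the written rule. For an isolated related ALT rise of 7 to 13 days, the listed response is review at Grade 2 and nothing at Grades 3 and 4. Review of the worse event is left to judgement while review of the milder one is mandatory.

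The expected frequency is low. At Amendment 4 ALT had not exceeded Grade 1, and no related Grade 2 event had lasted 7 days. The 6 remaining infusions are an upper bound from that date; by Amendments 5 and 6 there may have been fewer, and the documents do not give the number. No endpoint, estimate or analysis is affected.

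The conclusion rests on reading two consecutive weeks as 14 days (the gap is smaller on the two-sample reading) and on Amendment 6 having left the section unchanged. It makes no claim about rises under 7 days, which trigger nothing at any grade, and none that any subject was harmed. A reader might also take it as a case against the relaxed ALT halt. It is not: that change has its own stated rationale.

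**What to change.** In the DRB-review item of Section 9.3.3.1, insert *or higher* after *Grade 2*, and add that days at a higher grade count toward the 7 days. Leave the ALT halt at more than 5 × ULN for two consecutive weeks unchanged.

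The 7-to-13-day row then gives review at all three grades. For other related events of Grade 3 or above the change adds nothing, since they already halt enrolment. The counting clause is needed so that a rise moving between grades is not split into records each shorter than 7 days. The cost is one line of wording and at most a few extra DRB reviews.
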